- iii. A 10-point visual analog scale for anxiety (1 no anxiety, 10 worst anxiety)
  - 1. Hornblow 1976; Results suggest that VAS is sufficiently reliable to be used to assess acute pain.
- iv. Pain medication used pre/post traction pin placement
- v. Overall time required for placement of skeletal traction pin
- vi. Resident perception of procedural difficulty
- vii. Intermediary Newman-Keuls (SNK) analysis techniques will be utilized to regularly perform preliminary *post-hoc* tests. This will aid towards

*statistical analysis plan*

- i. T-Test of Sampling Demographic Data
- ii. T-test of Primary Outcome Measures between subject groups
  - 1. Pain Survey Scores
  - 2. Anxiety Survey Scores
  - 3. Experience Survey Scores
- iii. Linear & Logistic Regression Analysis of Primary Outcomes
  - 1. Addition of Demographic Covariates
  - 2. Observing both Linear & Non-Linear identities of the relationship.
- iv. T-Test of Secondary Outcome Measures between subject groups
  - 1. Perception of Difficulty
  - 2. Procedural Time
  - 3. Pain Medication
- v. Linear & Logistic Regression Analysis of Secondary Outcomes
  - 1. Addition of Demographic Covariates
  - 2. Observing both Linear & Non-Linear identities of the relationship
- vi. Power analysis or statement of precision

A power analysis was performed to estimate the minimum sample size needed to adequately detect a clinically significant change in anxiety and pain scores between the audio distraction groups. At a Type I error rate of 0.05 ( $\alpha=0.05$ ) and 80% power ( $\beta=0.80$ ), the power analysis identifies a minimum sample size of 42 total participants, 21 for each group. The estimated effect size is 2.0 on the utilized 10-point scale with a two-sided standard deviation of two. These measures for effect size are adopted from a previously performed colonoscopy audio distraction study which identified clinically significant results (Costa 2010). A power analysis for secondary outcome measures was not performed due to their non-inferential nature.
- vii. *Strengths*

1. Regions Hospital and Hennepin County Medical Center provides sufficient access to the study population and the facility is adequate to conduct the study. Both Level I Trauma centers.
2. Adequate qualified staff members to conduct the study
3. Staff will be adequately trained on the protocol and their specific research related duties.
4. Exhaustive primary & secondary outcome assessment.
5. Use of verified survey techniques.

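### The stated minimum of 42 participants at 80% power does not follow from the stated inputs, which need 34; either the calculation or an unreported input needs to be identified (minor, safe direction)

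*Combined protocol and SAP*

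**What the plan says.** All the relevant text is in the Combined protocol and SAP, Section 4 (Approach).

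- The statistical analysis plan, item vi, sets out to find the "minimum sample size needed to adequately detect a clinically significant change in anxiety and pain scores between the audio distraction groups".
- Error rates: "At a Type I error rate of 0.05", and power written as "80% power ( $\beta=0.80" (closing bracket omitted here).
- Effect and spread: "The estimated effect size is 2.0 on the utilized 10-point scale with a two-sided standard deviation of two".
- Source: "These measures for effect size are adopted from a previously performed colonoscopy audio distraction study which identified clinically significant results".
- Result: "the power analysis identifies a minimum sample size of 42 total participants, 21 for each group".

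Item ii of the same plan gives the analysis: "T-test of Primary Outcome Measures between subject groups", covering pain, anxiety and experience. The study design text gives equal allocation, in blocks of 10. Neither document part states a split of alpha, an allowance for lost participants, a non-parametric adjustment or the sidedness of the test. The words two-sided are attached to the standard deviation.

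**The concern.** A difference of 2.0 with an SD of 2 is a standardised difference of 1.0. At 80% power and alpha 0.05 that calls for well under 21 per group. A size described as the minimum for 80% power should be the smallest that reaches 80%, and here it is 8 participants larger.

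What is at stake is narrow. A reader cannot reproduce the sample size, does not know what power 42 participants really give, and cannot tell whether some of the 42 can be lost with the stated 80% still intact. If the missing input is a split alpha, the final tests would also have to use it, and the plan does not say so.

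**Working it through.** **Inputs** (Section 4): alpha 0.05; power 80%; difference 2.0; SD 2; two-sample t-test; 1:1 allocation. Standardised difference d = 2.0/2 = 1.0. Two-sided testing is my assumption; one-sided is tried as well.

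**Formula.** With n per group, df = 2n − 2 and noncentrality d × √(n/2). Power is the probability that a noncentral t variable exceeds the critical value t(1 − α/2, df) in absolute value (t(1 − α, df), upper tail only, if one-sided).

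**Attempt to reproduce 21 per group from the inputs as written**

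| Test | n per group for 80% | Power at that n | Power at one fewer |
|---|---|---|---|
| Two-sided t | 16.71, so 17 (34 total) | 80.7% | 78.1% |
| One-sided t | 13.10, so 14 (28 total) | 82.4% | 79.7% |
| Two-sided normal approximation | 15.70, so 16 (32 total) | – | – |

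None gives 21. The excess is 42 − 34 = 8 participants, and 8/34 = 23.5%.

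**Power at the stated size.** For n = 21: df = 40, noncentrality √10.5 = 3.240, critical value 2.021, power 88.5% (two-sided). The one-sided figure is 93.8%, further still from 80%.

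**Inputs that would give 21 per group by two-sided t-test but are not in the text**

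- Alpha 0.025 (0.05 split over pain and anxiety), SD 2: n = 20.32, so 21; power 81.5% at 21 and 79.3% at 20.
- A larger SD written as two, alpha 0.05: SD 2.20 needs 20.002 and SD 2.257 needs 20.996, so this range rounds up to 21. Power at 21 runs from 82.0% (SD 2.20) to 80.0% (SD 2.257). SD 2.258 needs 21.01, so 22.
- A loss allowance of about 19 to 20%: 17/0.81 = 20.99, 17 × 1.2 = 20.4 or 16.71/0.80 = 20.89, each rounded up to 21. The form 17/0.80 = 21.25 gives 22.

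The list is not exhaustive. For example, the normal approximation at alpha 0.0167 (three primary outcomes) gives 20.94, so 21.

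**What each would mean for a reserve**

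| Assumed basis | Power, 42 analysed | Power, 34 analysed |
|---|---|---|
| Inputs as written | 88.5% | 80.7% |
| Alpha 0.025, SD 2 | 81.5% | 71.2% |
| Alpha 0.05, SD 2.25 | 80.3% | 71.0% |

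Losing 8 of 42 is 19.0%. If a loss allowance was the basis, the first row applies and the reserve is real.

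**The case against.** The strongest reply is that nothing in the trial goes wrong. Under every explanation listed above, 42 analysed participants give at least the stated 80% power. No test, estimate or decision changes, and enrolment need not change. That stands, and it is why the point is minor.

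It can also be said that no mistake has been shown. The SD is given as a word without decimals, and values that round to two (1.5 to 2.49) need 10 to 26 per group, a range that contains 21. A conventional 20% allowance also reaches 21 in two of its usual forms. This stands too: a correct calculation with one input left out fits the text as well as a wrong calculation does. A reader might infer that the sponsor miscalculated, but the documents do not settle that. The SD comes from a cited colonoscopy study that is not in the Section 10 reference list, so its unrounded value cannot be checked here. Against the loss route, a size called the minimum needed sits awkwardly with an inflated one.

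A reader might also infer from the 71% figures that the trial is at risk of being underpowered. The documents do not support that. Those figures require both an undocumented input and the loss of 8 participants. The three VAS scores are collected once, right after the traction weight is hung, and the exclusions remove patients who cannot communicate or mark the scale. The Limitations list admits that the acute setting may restrict survey information, so some loss is possible, but nothing points to 19%.

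None of this makes the paragraph reproducible as written.

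**Conclusion.** The stated sample size and power do not match the stated inputs. With a two-sided t-test those inputs need 34 participants, against 42 stated, and 42 gives 88.5% power, against 80% stated. A one-sided test widens the gap. The arithmetic is firm given d = 1.0, 1:1 allocation and a t-test; the cause is open between a miscalculation and an unreported input.

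The discrepancy is in the safe direction. It does not show that the trial is too small, and it is no reason to cut enrolment to 34: if alpha 0.025 or an SD near 2.25 lies behind the figure, 42 is just about what 80% power requires. What remains unknown is the true planned power (80.0% to 88.5% across the explanations considered) and whether 42 includes a reserve for loss. Severity: minor.

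Two slips in the same paragraph carry no extra weight: beta is equated with 0.80 where power is meant, and two-sided describes the SD instead of the test.

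**What to change.** Keep 42. Then:

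1. Identify the input that produced 42 (alpha, unrounded SD, loss allowance or other) and restate item vi with that input, the sidedness of the test and the power it gives.
2. If it was a split alpha, use the same alpha in the final t-tests of the outcomes it covers, and say so in item ii.
3. Only if no other input was used, state: two-sided t-test, alpha 0.05, difference 2.0, SD 2; 34 participants give 80.7% power and 42 give 88.5%. Writing this without step 1 could claim 88.5% where the true basis gives about 80% to 82%.
4. Write beta = 0.20, attach two-sided to the test, and add the cited colonoscopy study to the reference list.

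The cost is the wording of one paragraph and a reference, plus a line in item ii if alpha was split. Enrolment, data collection and the timeline do not change.

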**6. Risks and Benefits**

- a. Potential risk factors with audio distraction group
  - i. Patient may not hear resident when attempting to communicate
    1. Resident will be able to communicate with an assistant in the room to get the attention of the patient, if needed.
  - ii. Patient may receive less pain management with the assumption they will have higher pain tolerance from the audio distraction
    1. Resident will continue to follow standard of care for traction pin placement
  - iii. Benefit for patient in audio distraction group to experience less discomfort during traction pin placement

- iv. Benefit to society, as this study may provide an opportunity for providers to decrease the level of discomfort in patients who need traction pin placement.

## 7. Data Confidentiality and Privacy

- a. In order to secure patient confidentiality and data security, all data will be de-identified. All patients will be assigned a research identification number (not their MRN) that cannot be associated with their name, birthdate, or other identifying information.
- b. Patient information will only be accessed via secure servers for Regions Hospital and on encrypted password-protected computers. If it is necessary to transmit patient data, it will be transmitted in the de-identified format, using only patient research identification numbers.
  - i. De-identified data will be shared with collaborating sites (HCMC)
- c. At the end of the study, the electronic files will be permanently deleted and patient identifiers will be removed. All hard copies will be shredded.

## 8. Timeline

- a. August 2017: IRB submission
- b. September 2017: IRB approval
- c. October 2017: Protocol implementation
- d. October 2017: Patient enrollment
- e. October 2018: Patient enrollment closes
- f. November 2018: Data analysis
- g. December 2018: Manuscript preparation
- h. February 2019: Manuscript submission

## 9. Dissemination/Sharing Results/Integration and Impact

- a. We do plan on publishing to peer reviewed orthopedic journals such as;
  - i. The Journal of Bone and Joint Surgery
  - ii. Clinical Orthopedics and Related Research
  - iii. Journal of Orthopedic Trauma
- b. We plan to disseminate the information on a local and regional level by presenting at;
  - i. University of Minnesota Grand Round
  - ii. Regions Department of Orthopedic Surgery Grand Rounds
  - iii. Minnesota Orthopedic Society poster presentation
  - iv. Mid-America Orthopedic Society poster presentation
- c. Results will be shared with HealthPartners
  - i. The results of this project could possibly change the stand of care for placing skeletal traction pins at Regions Hospital

